All participants were provided with three self-monitoring tools: a Yunmai Smart Scale for measuring body weight, a Fitbit Flex for monitoring physical activity, and the Fitbit app for recording food intake and viewing data from all three devices. Participants were told to weight themselves weekly in weeks 1-10 and daily thereafter; to wear the physical activity sensor daily, paying particular attention to "active minutes" when reviewing device data; and to record food intake daily. During Phase I, device data were not available to counselors. Participants were instructed not to share device data with friends, family, or other participants at any point in the program.

Phase II: Remote Maintenance Treatment

At the conclusion of Phase I, participants were randomly assigned (matching for initial weight loss) to one of two treatments for Phase II (weeks 13-52): standard lifestyle modification (LM) or lifestyle modification plus device data sharing (LM+SHARE). Phase II treatment was delivered remotely. There were no further group meetings; participants received monthly, individual, 15-minute phone calls and weekly, one-way text messages. Participants in both conditions were instructed to continue using digital devices daily to self-monitor weight, physical activity, and food intake.

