In LM+SHARE, counselors had access to a secure online portal that uploaded data from participants' self-monitoring devices. Counselors were instructed to attend to changes in weight, adherence to dietary intake and physical activity goals, and self-monitoring frequency when viewing data. In phone calls and text messages with participants, counselors used their data observations to cultivate a sense of supportive accountability, conveying to participants that they were regularly monitoring adherence to program goals in order to sustain participant success. Counselors set goals with participants in monthly phone calls, subsequently viewed data relevant to the goals to determine if they were being met, and in the text messages and phone calls that followed provided praise to reinforce positive behaviors or expressed concern if adherence was poor. For example, a text message might say: "I'm so impressed that you started recording your food intake again! I saw you recorded for 5 days this week. Reflect on how you accomplished that, and how it was helpful, so that you can carry this success forward. Keep up this fantastic work!" As another example, in a phone call a counselor might say: "You set a goal last month of 5 bouts of exercise per week, and I see that you only averaged 2 per week. Tell me more about what happened." Counselors also used phone calls and text messages to review core behavioral skills or strategies and encourage their use.

In the LM condition, counselors did not have access to device data. Counselors used participant self-report in monthly phone calls (prompted by questions such as, "How successful have you been in meeting your physical activity goals since our last call?") to assess progress and adherence. As in LM+SHARE, LM counselors reviewed one or more core behavioral skills or strategies in each phone call. All participants in the LM condition received standardized, weekly text messages that highlighted a core behavioral skill or strategy; messages in this condition were not personalized.

The seven counselors who provided treatment had degrees in psychology or a related field (1 = PhD, 4 = MA/MS, 2 = BA/BS). Counselors had previous training in behavioral weight loss and also completed a training workshop and weekly supervision for this study. All counselors provided both forms of treatment.

Measures

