Assessments were completed at weeks 0 (baseline), 13 (i.e., baseline of Phase II treatment), week 26, and week 52 (end of treatment).

Demographics. Age, gender, education, race, and ethnicity were self-reported at baseline.
Height and weight. At each assessment, research staff weighed participants using a Tanita
model WB-3000 digital scale. Participants were weighed in light street clothes without shoes.
Height was measured at baseline using a stadiometer. Measurements were taken twice and
averaged.

Physical Activity. Participants wore ActiGraph GT3X tri-axial, solid state accelerometers to measure MVPA at weeks 13 and 52. (To minimize "device burden," given that participants were asked upon enrollment to begin using three other self-monitoring devices, Actigraph measurements were not done at week 0.) Participants were told to wear the accelerometer for seven consecutive days during all waking hours, and data were considered valid when available for a minimum of four days for at least 10 hours per day. ActiLife software was used to calculate MVPA using established cut-points (16). Consistent with the intervention focus on bouted exercise, MVPA totals included only episodes of MVPA detected by the accelerometer to be \geq 10 minutes.

Self-monitoring engagement. Device data were collected on a secure online portal, which allowed for calculation of the percent of days during which weight was recorded on the Yunmai Smart Scale; \geq five foods were logged in the Fitbit app; and the Fitbit counted \geq 500 steps.

Treatment engagement. Engagement with treatment phone calls was calculated as the number of calls the participant completed during Phase II, out of 8 possible calls. The number of text messages sent by the counselor also was calculated.

Treatment satisfaction. Treatment satisfaction was measured using the Treatment Acceptability Questionnaire (17), with some items modified to reflect specific treatment components of the current study. This measure has good internal consistency and concurrent validity.

Perceived accountability. The "Perceptions of Accountability" subscale of the Supportive Accountability Scale (18) was administered to measure the extent to which the participants feel accountable to others to achieve their weight control goals. Reliability and validity for this scale has been established (18).

Data Analysis

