Retention was compared between the two conditions using Fisher's exact test. Permutation test was conducted to examine the difference between conditions in the number of phone calls and text messages (which could vary if a participant requested that contact be discontinued or temporarily suspended) and treatment acceptability ratings. Permutation test, a type of nonparametric test that uses sampling without replacement to test hypotheses, was chosen due to the violation of t-test assumptions in the data set (19). We conducted permutation based ANCOVA to compare self-monitoring engagement in Phase II between conditions controlling for Phase I self-monitoring engagement. This analytic method was implemented in the "permuco" package in R and has been shown to be robust to data with non-normal distribution (20). ANCOVA was used to test the difference in weight change between conditions, controlling for Phase I weight loss. Change in bouted MVPA during Phase II was compared between LM and LM+SHARE controlling for Fitbit-measured changes in Phase I MVPA using permutation based ANCOVA. One outlier for bouted MVPA at 13 weeks in the LM condition was removed from the analyses (MVPA was more than 3 SDs above others). Repeated measures ANCOVA was used to compare perceived accountability controlling for Phase I change. Analyses examined whether the effect of condition on weight loss during Phase II was mediated by change in monthly adherence to self-monitoring during the first 6 months of Phase II, or change in perceived accountability from weeks 13 to 26. If weight and MVPA outcome data were missing, the most recent data from the participant's digital scale or Fitbit, respectively, were used for imputation; if those data were not available, baseline data were carried forward. Strong associations were found between weight measured in clinic and via home digital scale (r= .995, p< .001 at 52 weeks), and between Actigraph and Fitbit measurements of MVPA (r = .60, p < .001 at 52 weeks), validating this missing data approach. The study was designed as a pilot randomized trial, with a focus on having a large enough sample for estimates of feasibility, acceptability, and effect sizes to be reliable. Data were analyzed in SPSS version 25 and R version 4.0.0.

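### The accountability mediator is a week 13-to-26 change with no stated adjustment for the week-13 level, so the indirect effect may be biased by an amount the documents do not allow one to fix

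*Combined protocol and SAP*

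**What the plan says.** All of this is in the combined protocol and SAP.

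- **Data Analysis**, on mediation: "Analyses examined whether the effect of condition on weight loss during Phase II was mediated by" either change in self-monitoring adherence or "change in perceived accountability from weeks 13 to 26". No equations, method or covariates are given for the mediation analysis.
- **Data Analysis**, neighbouring sentences: "Repeated measures ANCOVA was used to compare perceived accountability controlling for Phase I change", and for weight, "ANCOVA was used to test the difference in weight change between conditions, controlling for Phase I weight loss". Neither covariate is the week-13 accountability level, and the text does not say whether either was carried into the mediation models.
- **Measures**: the assessment schedule describes week "13 (i.e., baseline of Phase II treatment".
- **Phase II: Remote Maintenance Treatment**, on the timing of allocation: "At the conclusion of Phase I, participants were randomly assigned (matching for initial weight loss) to one of two treatments for Phase II". Of the data-sharing arm, the section says "counselors used their data observations to cultivate a sense of supportive accountability".

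**The concern.** The mediator is D = M26 − M13. A weight model that contains D but not M13 can fit only one pattern: the week-13 score must have a coefficient equal in size and opposite in sign to that of the week-26 score. Nothing in the documents justifies that constraint. The described mechanism, counselors fostering a feeling of accountability while treatment is under way, can be read as a state during Phase II at least as easily as a rise from week 13.

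If the state matters, D carries week-13 variation that is irrelevant to weight and is negatively related to D. The mediator-to-weight path is then misestimated, and so is the split of the condition effect into indirect and direct parts. Accountability is the mechanism the LM+SHARE arm was built to use. A weak or null indirect effect could therefore lead readers to discard it for a reason that lies in the model. This is bias, so a larger sample would not cure it.

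**Working it through.** **Inputs.** From the documents: the mediator definition, randomisation at the end of Phase I, and week 13 as the Phase II baseline. The documents give no sample size, no SD or between-week correlation for the accountability score, and no indirect effect. There is no plan figure to reproduce, and every value of k, r, effect size and sample size below is an assumption.

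**Step 1: condition-to-mediator path.** Week 13 is a pre-treatment baseline, so M13 is expected to balance between arms. The arm difference in D then estimates the same quantity, a, as the arm difference in M26. This path is unbiased with or without M13.

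**Step 2: mediator-to-weight path.** Let X be condition and Y Phase II weight change, and suppose Y = b·M26 + c·X + error. Scale the within-arm SD of M13 to 1, so that M26 has SD k, and let r be the within-arm correlation. Within arm:

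- cov(M26, D) = k² − rk
- var(D) = 1 + k² − 2rk

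Regressing Y on X and D gives slope b·f, with f = (k² − rk)/(1 + k² − 2rk). The indirect effect is a·b·f instead of a·b.

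**Step 3: numbers.**

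| k | r | calculation | f |
|---|---|---|---|
| 1 | any | (1 − r)/(2 − 2r) | 0.50 |
| 0.8 | 0.5 | 0.24/0.84 | 0.29 |
| 1.25 | 0.5 | 0.9375/1.3125 | 0.71 |
| 0.8 | 0.7 | 0.08/0.52 | 0.15 |
| 1.25 | 0.7 | 0.6875/0.8125 | 0.85 |
| 2 | 0.5 | 3/3 | 1.00 |
| 1.5 | 0.7 | 1.2/1.15 | 1.04 |
| 0.67 | 0.7 | −0.0201/0.5109 | −0.04 |

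The sign reverses when k < r. The factor exceeds 1 when rk > 1, that is, k > 1/r.

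**Step 4: other forms of dependence.**

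- If weight depends on the change itself, f = 1 and there is no bias.
- If weight depends on the mean of weeks 13 and 26, the retained share is (k² − 1)/(1 + k² − 2rk). This is 0 at k = 1. At r = 0.5 it is −0.36/0.84 = −0.43 for k = 0.8 and 0.5625/1.3125 = 0.43 for k = 1.25.
- If both weeks matter and k = 1, the slope on D is (b26 − b13)/2. With assumed b26 = −0.3 and b13 = −0.2 it is −0.05 instead of −0.30.
- If weight depends on the week-26 level, k = 1, and Phase I change in accountability is also a covariate, the share is 0.57 to 0.67 for r from 0.3 to 0.7.

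**Step 5: with M13 in both equations.** The share is 1.00 in closed form for dependence on the week-26 level, on the mean and on the change. It makes no difference whether M26 or D is then called the mediator. Since D = M26 − M13, once M13 is in the model both give the same coefficient on the mediator and the same condition effect on it.

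**Step 6: simulation check.** Weight was made to depend on the week-26 level (4,000 replicates, assumed total N of 60 and 100, a = 0.5, b = −0.4). At k = 1 the unadjusted share was 0.48 to 0.50. At r = 0.5 it was 0.28 to 0.29 for k = 0.8 and 0.72 for k = 1.25. With M13 added it was 0.97 to 1.01 in all settings.

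**Illustration of scale.** With assumed 40 per arm, r = 0.6, k = 1, a = 0.6 SD and b = −0.3, the indirect effect is 0.6 × (−0.3) = −0.18, and half of that, −0.09, with the change score alone. Simulated joint-significance power was about 50% and 18% respectively.

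**The case against.** The strongest reply is that the text specifies no mediation model at all. A reader might infer that the analysis used a raw change score with the week-13 level left out. The documents do not say so. They do not state whether the change was raw or residualised, or whether covariates from the neighbouring analyses were carried over. That stands: what can be shown is that no week-13 adjustment is described, not that none was made.

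A reader might also infer that the indirect effect is halved, or always pulled toward zero. Neither follows. One half needs equal within-arm SDs and dependence on the week-26 level alone, and the factor can exceed 1. Equal SDs are not assured, because week 13 follows weekly group contact and Phase II contact differs by arm.

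It can further be said that cultivating accountability is compatible with an increase being what matters, and that the outcome is itself a change, so a change-on-change model is coherent. That stands too: under that model there is no bias. But the adjusted model contains the change model as a special case, so adjusting does not require choosing between the two.

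Finally, this is a pilot, and testing a mediator for significance is not among its stated aims. This limits the weight of the power figures but not of the bias, since the plan says it wants its effect-size estimates to be dependable.

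**Conclusion.** The point holds in conditional form. As written, the mediator is a change score with no described adjustment for its Phase II baseline level. If Phase II weight change depends on the week-26 level, the indirect effect is multiplied by (k² − rk)/(1 + k² − 2rk): one half at equal SDs, about 0.15 to 0.85 over k = 0.8 to 1.25 and r = 0.5 to 0.7, near or above 1 for large k, and negative when k < r. The documents supply neither k nor r, so the actual size and direction cannot be stated, and it cannot be said that any reported mediation result is wrong. The calculation rests on linear models, balance at week 13 through randomisation, and no other confounding of accountability and weight.

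Only the indirect effect and its split from the direct effect are at issue. The total effect of condition on weight, retention and acceptability are unaffected. The change is worth making but does not threaten the trial's main comparisons.

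**What to change.** State both mediation equations, with week-13 accountability as a covariate in each:

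- mediator: M26 on condition and M13
- weight: Phase II weight change on condition, M26 and M13

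Say which other covariates enter, in particular whether Phase I weight loss is carried over from the main weight analysis. Report the unadjusted change-score mediation as a sensitivity analysis, and give the within-arm SDs at weeks 13 and 26 and their correlation so that readers can compute the factor themselves.

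The cost is one extra covariate, which must already be on file because the change score requires it. There is a slight loss of power if the pure change model is exactly true: 54% to 48% in the assumed setting of 40 per arm. The document is dated October 2020, follow-up ended in May 2019, and the analyses are described in the past tense. If the adjustment was not made, adding it is a post hoc reanalysis and should be labelled as such. If it was made, a sentence saying so is enough.

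### A missing clinic weight is replaced by a home-scale reading with no correction described, so any systematic home-minus-clinic difference enters the change score of imputed participants only, and the cited correlation cannot detect it

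*Combined protocol and SAP*

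**What the plan says.** The Data Analysis section fills a missing weight in two steps. First, "the most recent data from the participant's digital scale or Fitbit, respectively, were used for imputation"; then, "if those data were not available, baseline data were carried forward". No calibration, offset correction or differencing within one device is described for the home value.

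The two sources are measured differently. In the clinic, research staff use a Tanita scale, and "Participants were weighed in light street clothes without shoes" (Measures, Height and weight). The home value comes from "a Yunmai Smart Scale for measuring body weight" (Phase I section). For home weighing the documents fix only the frequency: "Participants were told to weight themselves weekly in weeks 1-10 and daily thereafter", with daily use to continue in Phase II. Clothing and time of day at home are not stated.

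The outcome is a difference between two weights: "ANCOVA was used to test the difference in weight change between conditions, controlling for Phase I weight loss" (Data Analysis). The list of assessments in Measures includes week "13 (i.e., baseline of Phase II treatment", so the reference for Phase II change is a clinic weight.

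The support given for the rule is this: "Strong associations were found between weight measured in clinic and via home digital scale (r= .995, p< .001 at 52 weeks". The section treats that correlation as validating the approach. It gives no mean difference and no limits of agreement.

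**The concern.** Substituting one scale for the other inside a change score requires that the two agree in kilograms. A high correlation shows only that they rank and space people in the same way. If home weights run systematically above or below clinic weights, because of the device, clothing or time of day, an imputed participant is measured one way at the start of Phase II and another way at the end. The gap is then counted as weight change. This happens even if the home reading is taken on the day of the missed visit, so it is separate from the question of how old the reading is.

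The documents name no primary outcome, but the pilot is meant to yield reliable effect sizes, and weight change is one of the outcomes compared. An offset would alter each arm's mean change and, if the home-imputed shares differ between arms, the arm difference too.

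**Working it through.** **Inputs from the documents.** The substitution rule, the clinic and home weighing conditions, the week-13 reference, and r = .995 at week 52. **Not in the documents, so assumed below:** the offset d (home minus clinic), the SD of body weight, and the share of each arm imputed from the home scale.

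**1. The plan's own figure.** The correlation cannot be recomputed without participant data. It is taken as given, and the question is what it implies.

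**2. What the rule does to a change score.** Write home = clinic + d + e, with e averaging zero.
- Attender: change = C52 − C13.
- Imputed: change = H52 − C13 = (C52 − C13) + d + e.

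A participant whose weight did not change is scored at 0 if seen and at d on average if imputed. Example with an assumed d of −1.0 kg and e = 0: C13 = 90.0, H52 = 89.0, scored change 89.0 − 90.0 = −1.0 kg, true change 0. The same holds if change is counted from week 0, which is also a clinic weight. It does not apply where baseline is carried forward. The offset cancels from Phase II change if the week-13 weight was itself a home reading.

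**3. Can r = .995 detect d?** Adding a constant changes neither the covariance nor the SDs, so corr(C, C + d + e) = corr(C, C + e). A simulation of 100,000 pairs confirms this. With assumed weight SDs of 12, 15 and 20 kg and d of 0, −0.5, −1 and −2 kg, r was .995 in all twelve cases, while the mean home-minus-clinic difference equalled d to within 0.01 kg.

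**4. Scatter left at r = .995.** Discrepancy SD = SD × √(1 − .995²) = SD × 0.0999. This is 1.2, 1.5 and 2.0 kg for assumed weight SDs of 12, 15 and 20 kg.

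**5. Effect on the arms.** Shift in an arm's mean = d × its home-imputed share p. Shift in the difference (LM+SHARE minus LM) = d × (p_SHARE − p_LM). All d and p are assumptions.

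| d (kg) | p_SHARE / p_LM | LM+SHARE mean | LM mean | Arm difference |
|---|---|---|---|---|
| −1.0 | 10% / 10% | −0.10 | −0.10 | 0 |
| −0.5 | 20% / 10% | −0.10 | −0.05 | −0.05 |
| −1.0 | 20% / 10% | −0.20 | −0.10 | −0.10 |
| −1.5 | 20% / 10% | −0.30 | −0.15 | −0.15 |
| −1.0 | 10% / 20% | −0.10 | −0.20 | +0.10 |
| +1.0 | 20% / 10% | +0.20 | +0.10 | +0.10 |
| −2.0 | 30% / 10% | −0.60 | −0.20 | −0.40 |

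**6. Imputing within one device.** Imputed weight = C13 + (H52 − H13), so imputed change = H52 − H13 = (C52 − C13) + (e52 − e13). Both d and C13 drop out. If a share s of the discrepancy variance is a stable personal offset, the error SD with single readings is 1.5 × √(2(1 − s)) at an assumed weight SD of 15 kg: 1.06 kg at s = .75, 1.50 at .5 and 1.84 at .25, against 1.5 under the present rule. If the random part lies in the home readings and is independent between days, averaging three readings at each end reduces 1.84 to 1.84/√3 = 1.06 kg.

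**The case against.** The strongest reply is that the offset is assumed, not shown. The documents report no home-clinic mean difference. Silence about home clothing does not show that conditions differed, and d could be near zero or of either sign. That the home value goes in uncorrected is the plain reading of a text that mentions no correction; the text does not say so outright. This all stands and limits the point to an error that the plan leaves unchecked.

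A reader might go further and infer a bias in favour of LM+SHARE: its counselors follow self-monitoring frequency, so more home readings would exist for missed visits in that arm. The documents do not support this. Every participant in both arms received a scale and was told to weigh from week 1, and the rule sets no age limit on the most recent reading. Nearly anyone who used the scale therefore has a value. More frequent weighing makes the reading fresher but hardly affects whether one exists. The home-imputed share then depends mainly on missed clinic visits, and nothing indicates which arm missed more. The direction also needs home weights to run lower, which is not stated.

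Size is a fair objection as well. Against an assumed SD of Phase II change of 5 to 7 kg, a shift of 0.05 to 0.15 kg in the arm difference is about 0.01 to 0.03 SD.

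The last objection is that differencing can add noise. It can, by 22% at s = .25 with single readings (1.84/1.5 = 1.22), but averaging readings counters this. Noise in the week-13 clinic weight is no argument against the remedy, because that weight cancels from the imputed change.

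**Conclusion.** The point holds as a defect in the imputation rule and in its stated validation. As written, the rule puts any systematic home-minus-clinic difference wholly into the change scores of home-imputed participants, and r = .995 is no evidence that this difference is zero.

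Neither the size nor the sign of d can be established from the documents, nor can the number imputed per arm. Arm means shift even with equal shares. The between-arm contrast shifts only if the shares, or the offsets, differ by arm, and then in an unknown direction. With a common offset of an assumed |d| of 0.5 to 1.5 kg and an assumed 10-point difference in shares, it moves by 0.05 to 0.15 kg; larger assumed values give up to 0.40 kg. The likely effect is small. The change is still worth making because it is cheap, uses data already held, and removes a stable device or clothing offset. A claim that the result is biased towards LM+SHARE, or that home weights are known to be lower, goes beyond the documents.

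**What to change.** In Data Analysis, replace the weight rule as follows.

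- Imputed clinic weight = week-13 clinic weight + (mean of home readings near the missed visit, or of the most recent ones, minus mean of home readings near week 13). Daily weighing was instructed after week 10, so readings near week 13 should usually exist.
- If there is no home reading near week 13, add to the home value the mean clinic-minus-home difference from paired readings, pooled over arms. These pairs come from people who attended, so applying the difference to non-attenders is an assumption to state.
- In place of the correlation, report the paired mean difference and limits of agreement. The pairs behind r = .995 already exist.
- Report the number imputed from the home scale in each arm.
- Keep the present rule as a sensitivity analysis.

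Follow-up was complete by May 2019, so this is a re-analysis: a few lines of code and a short text change, with no new data. The cost is a little more noise if the home-clinic discrepancy is mostly random, limited by averaging several home readings. It does not cure an old last reading, which is a separate matter.

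### A missing Phase II weight takes the latest home-scale reading of any age and bypasses the week-26 clinic weight; r = .995 does not validate that rule for old readings

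*Combined protocol and SAP*

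**What the plan says.** The rule is in the Data Analysis section. It begins "If weight and MVPA outcome data were missing, the most recent data from the" participant's device, and continues "digital scale or Fitbit, respectively, were used for imputation; if those data were not available, baseline data were carried forward". The order for weight is therefore home scale first, baseline second. The section states no maximum age and no window around the missed visit.

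The rule is defended in the next sentence: "Strong associations were found between weight measured in clinic and via home digital scale", with r = .995 at 52 weeks, described as "validating this missing data approach".

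The imputed values feed the main weight comparison: "ANCOVA was used to test the difference in weight change between conditions, controlling for Phase I weight loss".

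The Measures section lists assessments at weeks 0, 13, 26 and 52 and has staff weighing participants at each one, so a week-26 clinic weight exists for everyone who attended. That section attaches the word baseline to week 0 and also, as the baseline of Phase II treatment, to week 13.

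**The concern.** Phase II is the maintenance phase, so weight change over weeks 13-52 is the quantity of interest. A carried-forward reading erases whatever happened after it was taken. Three features of the text make this more than a formality.

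- **Order of sources.** Someone who stopped home weighing at week 18 but attended week 26 would, as written, have the week-18 home value used at week 52. Someone with no home data would go to baseline even with a week-26 clinic weight on file.
- **The evidence offered.** Agreement between two scales at week 52 is a different property from stability of weight over the preceding weeks. The plan treats the first as proof of the second.
- **The fallback.** If baseline means week 0, the rule imputes full reversal of Phase I loss. If it means week 13, it imputes no Phase II change.

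The plan foresees incomplete data. It says "Retention was compared between the two conditions using" an exact test, and that contacts "could vary if a participant requested that contact be discontinued or temporarily suspended". A stated aim of the pilot is a sample large enough for "estimates of feasibility, acceptability, and effect sizes to be reliable", and the weight effect is one of those effect sizes.

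**Working it through.** **The plan's own figure.** r = .995 is an observed result and cannot be recomputed without participant data. What can be checked is what it is able to show.

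1. A correlation at 52 weeks needs a week-52 clinic weight, so nobody imputed at week 52 contributes to it.
2. It does not change if every home reading is off by a constant.
3. It does not respond to the age of carried values. In a simulation with assumed weight SD 15 kg, mean regain 0.10 kg per week and 20% missing, r among people with both readings stayed at .995 throughout:

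| Age of carried value (weeks) | Mean error in imputed people (kg) | r of carried value with true week-52 weight |
|---|---|---|
| 0 | 0.0 | .995 |
| 26 | -2.6 | .98 |
| 39 | -3.9 | .96 |

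By formula, an old reading correlates s/√(s² + d²) with current weight, where s is the between-person SD and d the SD of individual change since the reading. For s = 12-20 kg and d = 3-5 kg this runs from 12/√(144 + 25) = .92 to 20/√(400 + 9) = .99. A high r is thus compatible with a large mean error.

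**Error per imputed person.** Inputs: Phase II is 52 - 13 = 39 weeks (documents); linear regain R of 3 or 5 kg over Phase II (assumed); last home weight at week w (assumed). Missed regain = R × (52 - w)/39. Cost of bypassing the week-26 clinic weight = R × (26 - w)/39.

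| Reading used | Missed regain, R = 3 / 5 (kg) | Cost of bypassing week 26 (kg) |
|---|---|---|
| Home, week 14 | 2.92 / 4.87 | 0.92 / 1.54 |
| Home, week 20 | 2.46 / 4.10 | 0.46 / 0.77 |
| Home, week 25 | 2.08 / 3.46 | 0.08 / 0.13 |
| Clinic, week 26 | 2.00 / 3.33 | - |
| Home, week 40 | 0.92 / 1.54 | none; the home value is better |

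With no change in weight the error is 0. With a further loss of 2 kg it reverses: -2 × 32/39 = -1.64 kg at week 20.

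**Arm mean.** Assume a share m of 10-20% misses week 52, all with a last home weight spread evenly over weeks 14-25 (mean 19.5, so 32.5 weeks stale). Understated regain = m × R × 32.5/39, from 0.10 × 3 × 0.833 = 0.25 kg to 0.20 × 5 × 0.833 = 0.83 kg. With week-26 clinic weights instead it is m × R × 26/39 = 0.20 to 0.67 kg. Reordering the sources therefore recovers about a fifth.

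**Arm difference, equal staleness.** If a true difference of 2 kg builds up linearly, the expected difference is 2 × (1 - m × 32.5/39):

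- m = .10: 2 × (1 - 0.0833) = 1.83 kg
- m = .20: 2 × (1 - 0.1667) = 1.67 kg

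Simulation with 40 per arm, SD of regain 5 kg and scale noise 1 kg (all assumed) gave 1.82-1.84 and 1.66-1.68 kg.

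**Arm difference, unequal staleness.** The added bias is m × R × gap/39. For each 10% missing and 10-week gap this is 0.10 × 3 × 10/39 = 0.08 to 0.10 × 5 × 10/39 = 0.13 kg, sign unknown. It is a unit of scale, not a bound.

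**Fallback.** For a Phase I loss of L kg, week 0 imputes a Phase II gain of L and week 13 imputes 0. The two readings of the word differ by L for each person who reaches this step. Under the week-0 reading the error can run opposite to that from a stale home value.

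**The case against.** The strongest reply is that nothing shows the problem occurred. Both arms were told to weigh daily, the documents give no count or age of imputed weights, and the analysts may have applied an unwritten window. A home weight taken shortly before a missed visit is a good substitute, and there r = .995 is relevant support. All of this stands. It limits the size of the concern, but not the reading of the rule or of the correlation.

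The 10-20% missing, all last weighed at home in weeks 14-25, is a deliberately unfavourable case with no support in the documents. Two limits on the correlation argument also stand: a person imputed only at week 26 can still contribute to r at week 52, and the plan does not say how close in time the paired readings were.

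A model is not a complete cure. Multiple imputation looks unbiased when data are simulated as missing at random. In an illustrative not-at-random case (about 14% missing, true mean regain 3 kg), model-based imputation gave 2.33 kg and the early carried value 2.07 kg, so most of the error remained.

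Stronger readings that a reader might infer are not supported:

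- **That standard errors are too small because filled values count as observed.** Each filled value is the participant's own reading. With no true difference, simulated model standard errors (1.04-1.10) matched the estimator's own spread (1.02-1.11), and type I error was 4.5-5.4%.
- **That the rule favours one arm.** LM+SHARE counselors could see self-monitoring frequency and LM counselors could not, so staleness might differ. That is a mechanism, not evidence.
- **That equal staleness makes the comparison safe.** This holds only when there is no true difference.

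**Conclusion.** The point holds for the rule as written. It sets no age limit, omits the week-26 clinic weight, leaves the baseline week open, and rests on a correlation that does not address old readings.

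The consequence for the arm comparison is shrinkage toward zero when weight is changing and a real difference exists: 2 kg becomes about 1.7-1.8 kg under the assumed inputs. Unequal staleness could add bias of either sign. The actual size is unknown and may be near zero. Confidence is high for what the rule says and for what r cannot show, and low for the size of any bias. This should be fixed, but the documents do not show that the trial's weight result is wrong.

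**What to change.** 1. If a single-value rule is kept, use the latest post-randomisation weight from either source, clinic or home, at or before the missed visit. State whether baseline means week 0 or week 13. If a window was applied in practice, write it down.
2. Add a mixed model or multiple imputation using all clinic and home weights, arm and Phase I loss, with a not-at-random sensitivity analysis. Show the present rule alongside.
3. Report by arm the number, source and age in weeks of imputed weights. Limit the validation sentence to home readings taken close to the visit.
4. Label these analyses post hoc: follow-up ended in May 2019 and the document is dated October 30, 2020.

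The cost is a few lines of text, one table and a re-analysis of data already held. The downsides are a missing-at-random assumption in the main model, possibly wider intervals, and the post-hoc label. Item 1 alone is cheap but recovers only about a fifth of the error in the unfavourable case, so items 2 and 3 carry most of the value.
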